8.2 Assignment to Groups

For the dose-escalating, open label, randomized, pilot study in Sotuba/Bamako, the study will be randomized and then enrolled on a first available basis in the following manner:

1. Arms 1a and 2a, n=10; then
2. Arm 3a, n=5; then
3. Arms 1b, 2b, 4a; n=30; then
4. Arms 3b, 4b; n=20

For the field site (Bancoumana and Doneguebougou), the study will be enrolled in the following manner in a double-blind, en-bloc randomization and stratification by village within each of the following groups:

1. Arms 2c, 2d, 4c, n=240

Enrollment and randomization of subjects into the TBV portion of the double blind, randomized study in Bancoumana and Doenguebougou, Mali, as specified above and in **Section 14.6**, will

not occur until at least two vaccinations (Pfs25M and Pfs230D1M) have been administered to the corresponding arms in the Bamako/Sotuba, Mali (see [Appendix A](#)).

Enrollment occurs with receipt of the first vaccination. Subjects who are screened but not enrolled and/or randomized may be replaced.

8.3 Study Subject Schedule

Day to day study schedule will be completed as outlined in [Appendix B](#) and [Appendix C](#).

9 Study Procedures/Evaluations

9.1 Photographs of Rash or Injection Site Reactions

If a subject develops a rash or injection site reaction, photographs may be taken by the investigators. These photographs will not include the subject's face or any identifying scars, marks, or tattoos.

9.2 Clinical Laboratory Testing

Using standard techniques, the clinical laboratory will perform the following tests:

1. Complete blood count (CBC) plus white blood cell differential and platelet count.
 - The following CBC parameters will be assessed for safety throughout the trial: white blood cell count (WBC), absolute neutrophil count (ANC)/absolute granulocyte count (AGC), hemoglobin (Hgb), and platelet count (plt).
2. Serum creatinine (Cr).
3. Alanine aminotransferase (ALT).
4. HBsAg test (can include rapid diagnostics, ELISA, PCR if indicated).
5. HCV test (can include rapid diagnostics, ELISA, PCR if indicated).
6. HIV test (can include rapid diagnostics, ELISA, Western Blot if indicated).
7. Urine dipstick/Urinalysis (at screening only).
8. Urine and/or serum pregnancy testing (β -hCG).

Schistosomiasis testing (urine microscopic examination for *S. haematobium* and stool PCR for *S. mansoni*) and helminth testing (stool PCR for 8 common gastrointestinal parasite pathogens) will be completed in subjects enrolled in Arms 2c, 2d, 4c on Study Day 0. Test results will be available to the clinical trial sites, and if subjects did not receive the mass drug administration as expected since testing, individuals will be treated.

Urine microscopy for *S. haematobium* will be completed on site and results made available to the study team and subjects in real time. Subjects who test positive for *S. haematobium* will be offered treatment with praziquantel upon diagnosis. Stool results for helminth testing, which are being conducted on a research basis, will be provided retrospectively to the study site once completed, which may be after the completion of the study, and will be handled on a case by case basis for treatment indications of asymptomatic carriage. Positive results from either of these tests (stool or urine) will not be exclusionary for enrollment.

9.3 Malaria Diagnostics

9.3.1 Blood Smears

The gold standard for malaria diagnosis and evaluation of vaccine efficacy endpoints is the detection of malaria parasites on Giemsa-stained thick blood films. Giemsa stained thick and thin films will be examined for asexual and sexual parasites in the MRTC clinical laboratory, as outlined in [Appendix B](#). Blood smears are prepared in duplicate according to standard procedures and evaluated by trained study microscopists.

For detection of gametocytemia, each blood smear is read by two independent trained microscopists and is reported per 1,000 WBC. A positive gametocyte read is defined as a single, confirmed gametocyte seen by one reader and confirmed by the other microscopist per 1,000 WBC.

Thick blood smears may be prepared from the blood remaining in the IV cannula, or (at time points when no IV blood collection is planned) from a finger prick or venous blood sample at the subject's request.

Thin/thick blood smears will be used for diagnosis throughout the study.

9.3.1.1 Symptomatic Malaria

Clinical or symptomatic malaria for this study is defined as the presence of asexual *P. falciparum* parasites at any parasitemia with either an axillary temperature of ≥ 37.5 °C or more of the following symptoms: headache, myalgia, arthralgia, malaise, nausea, dizziness, or abdominal pain and will be reported as an AE.

9.3.2 Rapid Diagnostics

For unscheduled visits and clinical diagnostics, rapid diagnostic tests may be utilized for determination of an acute malarial illness; however, they cannot be used in place of microscopy for determination of parasitemia status for DSF.

9.3.3 Malaria PCR

While detection of parasites on thick blood smears remains the most common primary endpoint in human challenge trials, both PCR- and nucleic acid sequence-based amplification (NASBA)-based methods have been increasingly used to support blood smear data in malaria vaccine trials^{29,30}. These research molecular assays have significantly increased sensitivity for detection of *P. falciparum* blood-stage infection approaching 20 parasites/mL, often resulting in diagnosis 2-4 days earlier than by paired thick blood smears.³¹⁻³³ Quantification of parasite density by these methods allows evaluation of parasite growth curves for assessing the utility of partially-effective vaccine candidates. LMIV has also developed a research qPCR that detects 18s of *P. falciparum* with a detection limit of at least 500 parasites/mL that will be used during the study for comparison to traditional thick blood smears.

P. falciparum qPCR may be performed from all scheduled visits with a malaria blood smear noted (see [Appendix B](#)) to capture infections that remain below the detection limit for microscopy. For subject convenience, a finger prick sample can be used for both preparation of the microscopy slide and for DNA preservation, but venous blood draws can also be used.

9.3.4 Malaria Clinical Management

In accordance with the Malian Government treatment guidelines, subjects will be treated with approved anti-malarial treatment, such as artemether/ lumefantrine (Coartem[®], 80mg/480 mg per dose) or artesunate/amodiaquine (ASAQ; fixed dose artemisinin based combination therapy) that is indicated and approved for the management of uncomplicated *P. falciparum* malaria. Clinical or symptomatic malaria for this study is defined in [Section 9.3.1.1](#).

9.4 Immunologic Laboratory Testing

9.4.1 Antibody Assay

Anti-Pfs25, anti-Pfs230 ELISAs, anti-CSP, and anti-HBsAg will be performed on sera or plasma obtained from immunized subjects at LMIV in Bethesda, Maryland and may also be performed at collaborating laboratories.

For Pfs25 and Pfs230, briefly, microwell plates are coated with antigen solution. Plates are washed with TRIS-buffered saline (TBS) containing Tween-20 (T-TBS) and blocked with TBS containing skim milk powder. After washing with T-TBS, diluted serum samples are added in triplicate and incubated at room temperature for 2 hours. After incubation, unbound antibodies are removed by washing the plates with T-TBS, and alkaline phosphatase-conjugated goat anti-human IgG solution is added to each well and incubated for 2 hours at room temperature. Plates are then washed with T-TBS, followed by adding phosphatase substrate solution to each well; the plates are then covered and incubated for 20 minutes at room temperature for color development. The plates are read immediately at 405 nm with a microplate reader. The optical

density values are used to determine antibody levels by comparing to a standard curve generated from a known positive-control plasma included on each ELISA plate.

Additionally, the magnitude and kinetics of IgG responses may be explored over time post Vaccination #3. Quality of antibody responses may be explored via antibody avidity as well as assessment of antibody subclasses to provide useful insight into the humoral immune response.

9.4.2 B-Cell and T-Cell Assays

Specimens collected for B-cell and T-cell studies will undergo initial processing and cell separation at the clinical site and will be transported to LMIV according to standard procedures.

B-cell studies will be done at LMIV and associated immunology laboratory partners (MVI PATH, Adaptive Biotechnologies, Atreca). The analysis of the generation and maintenance of antigen-specific memory B cells will be carried out to determine if these cells can be elicited and maintained by vaccination. Peripheral blood lymphocytes will be obtained and assayed for the presence of antigen-specific memory B cells, total number of memory B cells, and plasmablast responses using flow cytometry and ELISPOT assays.

T-cell studies will be performed at LMIV. Antigen-specific T-cell responses to vaccination will be determined by ELISPOT and/or intracellular cytokine staining flow cytometry.

Ex vivo studies will be performed at MRTC using whole blood to enumerate various immune subsets (T, B, NK cells) prior to and after each vaccination.

9.4.3 Transcriptional Profiling

Whole genome transcriptional profiling will be performed to explore possible gene expression profiles or pathways that predict optimal responses to vaccination and to determine if innate immune responses are sensitively reflected in the PBMC transcriptome shortly after vaccination. Gene expression profiling following vaccination will allow the predictive capacity of eventual high and low responders, and thus will assist in defining the correlates of protection induced by vaccination.

Transcriptional analyses will be performed on whole blood collected as outlined in [Appendix B](#). Blood will be collected via venous puncture and placed in PAXGene tubes to preserve RNA integrity until the RNA is extracted. Specimens will be analyzed at the Research Technologies Branch, NIAID and/or the NIH Intramural Sequencing Center. The molecular profiling encompasses the identification of RNA transcripts present in all humans, which are induced or repressed after each vaccination. This does not represent genetic testing of individuals or their DNA.

9.4.4 Transmission-Blocking Assays/Evaluations

The transmission-blocking assays which will be conducted are summarized in [Table 13](#).

Table 13: Transmission Blocking Assays

Assay	Mosquitoes	Test Samples	Site
Standard Membrane-Feeding Assay (SMFA)	Lab strain (A. stephensi)	Membrane feeds with lab cultured parasites mixed with test serum/plasma/IgG	LMIV LMVR
Direct Skin Feed (DSF)	MRTC lab colonies (A. gambiae)	Direct skin feeds on vaccinees	MRTC

Feeding assays demonstrate biologic activity of transmission-blocking antibodies, and are critical to selection of transmission-blocking vaccine candidates. Subjects will be screened periodically by blood smear (as seen in [Appendix B](#)) for the presence of asexual parasites and gametocytes. Priority for feeding assays (SMFA and DSF) will be conducted post Vaccination #3 when gametocyte carriage and parasite carriage rates are the highest and antibodies secondary to Pfs230D1M are expected to be peaking post vaccination.

Multiple feeds might be conducted on a single subject at the multiple screening time points, but a single subject will not undergo more than 32 DSFs (inclusive of the twice a week feeds during the intense DSF period following Vaccination #3 and #4) following a vaccination.

9.4.4.1 Standard Membrane-Feeding Assay

Membrane-feeding assays demonstrate biologic activity of transmission-blocking antibody and are critical to selection of vaccine candidates. SMFAs will be performed on blood obtained at baseline and periodically after vaccination as outlined in [Appendix B](#). In a SMFA, test serum or plasma obtained from immunized subjects is mixed with parasites from a laboratory culture and the mixture is placed in a feeding cup covered with an artificial membrane. Pre-starved mosquitoes from a laboratory colony are allowed to feed through the membrane. A similar procedure is carried out on a malaria-naïve control serum at the same time using mosquitoes raised from the same laboratory colony. One week after the feed, mosquitoes are dissected and midguts are stained with mercurochrome for the oocyst form of the parasite. The reduction of the proportion of oocyst-laden mosquitoes or the reduction of average oocyst numbers per mosquito compared to mosquitoes fed on the control group demonstrate biologic function of the antibody, and may be predictive of efficacy in the field. SMFA results have been shown to correlate with ELISA antibody titers against Pfs25 in several species.²⁴ The SMFAs will be conducted at LMIV and LMVR in Rockville, Maryland.

At the time of the direct-feeding assays, venous blood may be collected from each subject as outlined in [Appendix B](#). The blood aliquot will be processed immediately for SMFA. The

process will be maintained at approximately 37°C to avoid temperature-induced gametogenesis. SMFA will be conducted at LMIV using laboratory-strain mosquitoes and parasites. Assays will compare feedings with:

- Plasma/sera;
- IgGs purified from the selected plasma/sera, mixed with a malaria-naïve human sera pool (to eliminate non-specific factors which may be present in plasma).

To confirm anti-Pfs25-specific and anti-Pfs230-specific transmission-blocking activities, SMFAs may also be conducted

- using Pfs25-specific and Pfs230-specific IgG purified using affinity chromatography;
- using test plasma/sera that has been depleted of Pfs25-specific and Pfs230-specific antibodies using recombinant Pfs25 and Pfs230 proteins.

9.4.4.2 Direct Skin Feeds

While the SMFA is standardized and reproducible and has been shown to correlate with ELISA antibody titers in several species, the parasite strain, gametocyte load in the feeder, and lab colony mosquitoes are all significantly different from those found under field conditions.²⁴ DSFs, in which insectary-raised clean mosquitoes are directly fed on infected individuals, we believe may be more likely to be predictive of an intervention's impact on transmission than membrane feeds. Thousands of subjects in Bancoumana or neighboring areas have previously been enrolled in direct-feeding tests without significant adverse effects reported. In 1994 and 1995, Toure and colleagues conducted direct feeds on 72 children aged 2 years or more without any risks identified.³⁴ From 1996 to 1998, Diallo and colleagues conducted DSFs on 372 children aged 4 to 18 years without any safety problems.²⁶ In 2002 and 2003, DSFs were carried out in Bancoumana and in a neighboring village on a total of 44 gametocyte carriers aged 6 to 18 years old,³⁵ also without any reported safety problems.

More recently, under four previously conducted clinical trials (NIAID Protocol #13-I-N109, #11-I-N143, #14-I-N159, #15-I-0044) the study team has performed over 2000 DSFs on subjects older than 5 years since June 2011. All DSF participants were actively followed 24 hours post feed and as many as 12 DSFs over a 2 week period have been conducted. Except for 1 case of definitely related Grade 2 erythema that resolved within 48 hours and 2 episodes of definitely related Grade 1 pruritus, there have been no other expected or unexpected AEs recorded as definitely, probably, or possibly related to the feeding procedures in either study. Additionally, under this protocol (#17-I-N006), 3518 DSFs have been completed with only four pruritus AEs (4/3518, 0.1%) in three subjects have been reported related to the DSFs. All have been mild (Grade 1), all starting on the day of DSF, and all resolved within 2 days. None of the DSF related AEs have met criteria for withdrawal of the subject from participating in future DSFs.

Additionally, under protocol #11-I-N143, multiple DSFs during a 24 hour period have been completed in 18 subjects to date. In these 18 subjects, there have been no reported AEs secondary to having multiple direct skin feeds completed in a short period of time and have been tolerated well by the involved subjects.

For DSFs, 2 feeding pints with approximately 30 pre-starved female mosquitoes in each will be prepared. Each subject will be exposed to the feeding pints for 15-20 minutes. All subjects will be offered a topical antihistamine and/or topical antipruritic to use following the feeds. Systemic medications may also be prescribed for treatment of local or systemic symptoms following DSFs if clinically indicated.

During the time periods outside of the intense twice a week DSF for approximately 12 weeks following Vaccinations #3 attempts to identify and optimize parameters that contribute to DSF variability may be implemented during the conduct of the feeding assays. Subjects will be provided the details of the variation on the DSFs prior to participation and are not required to deviate from the standard DSF (2 feeding pints; approximately 30 pre-starved female mosquitoes per pint; application to the bilateral calves or arms; exposure for 15-20 minutes; feed conducted at subject's convenience, usually dusk or dawn).

These variables include the following:

- Body location (for example, ankle, leg, forearm),
- Number of cups applied (for example, 2 cups or 3 cups),
- Time of day feeds conducted (for example, dawn, dusk, late night),
- Number of feeds per day (up to 2 feeds in a single calendar day),
- Duration of feeds (for example, decreasing time to 10 minutes).

The total number of mosquitoes used for each DSF will be maintained at appropriately 60 mosquitoes total regardless of these variables, and no subject will undergo more than 32 DSFs within any 6 month period post vaccination. Note, if subjects are not willing to undergo twice a week feeds at the time of the DSF, they will not be withdrawn but will be followed per protocol but with periodic DSF or without DSF being completed.

Previously, DSFs started either 1 or 2 weeks post vaccination in order to time the DSFs with expected peak antibody responses. Although antibody responses have significantly improved, in peak and more importantly durability, the question of functional activity no longer is focused on peak time periods, but rather duration of activity, we will still plan to start DSFs 1 week after vaccination #4 in order to assess activity early in the transmission season. DSFs will continue

twice a week for 16 weeks in order to increase timepoints available for analysis to evaluate vaccine efficacy.

Some experiments have already been completed under protocols #13-I-N109 and #11-I-N143 to try to help determine which time of day and body part will maximize positive DSFs. Although there was not a significant difference found between location and time of feed in this small experiment, we did find that feeding at dawn and on the arm were estimated to have the highest counts. The data collected under this protocol will provide additional information about how to optimize/maximize the DSF procedure.

After the feed, surviving mosquitoes will be assessed for infectiousness by microscopy or molecular assays.

9.4.4.2.1 Withdrawal from DSFs

The following criteria will be checked prior to each DSF and are contraindications to DSFs:

- Severe local or systemic reaction to mosquito bites following a previous DSF.
- Positive urine or serum β -hCG test (pregnancy testing results obtained within the last 7-10 days before the DSF are acceptable; see [Appendix B](#)).
- Acute illness with an oral temperature $>37.5^{\circ}\text{C}$ at the time of the DSF.
- Any other condition that in the opinion of the Investigator poses a threat to the individual if he/she undergoes DSF or that may complicate interpretation of the safety of DSF.

Recent use of antimalarial medications is not a contraindication to participating in the DSFs. The medication used and time period the medication was taken should be recorded on the subject's source documents and case report forms accordingly.

9.5 Entomological Procedures and Insectary Used in DSF

9.5.1 Mosquito Collection

Mosquitoes may be collected from residences or compounds or communities of study subjects on a periodic basis to assess mosquito infection rates and their relation to the transmission-blocking activity measured in blood samples as described above from consented subjects.

9.5.2 Mosquito Rearing at the Insectary

A laboratory colony of *A gambiae* established from a local catch in 2008 will be used for the DSFs. This colony has been used in the current assay development study, and was demonstrated to have similar susceptibility as the F1 progeny of the wild-caught mosquitoes. The colony has been maintained using blood meals collected under standard procedures of the blood transfusion center from local healthy donors. To ensure that the donor is free of potentially transovarial arbovirus in incubation, the donated blood is only used 5-7 days after the collection and after the

donor is confirmed to remain healthy during this period. Potentially transovarial arbovirus in mosquitoes or in blood meals may be detected by ELISA and PCR methods. However, it is not feasible to conduct these tests routinely on blood donor volunteers due to highly restricted access to positive controls required in these tests, but blood samples from donors and mosquitoes from the colony are tested for RVF on a regular basis in the US.

The insectary in which mosquitoes are reared in Bamako has been in use for more than 15 years. Security is ensured by the use of double doors, which prevents the escape of reared mosquitoes as well as the entry of non-insectary mosquitoes. Mosquitoes are transported to Bancoumana or Doneguebougou in net-sealed feeding cups secured in wooden holders inside a cooler, with wet towels to maintain adequate humidity. After arrival at the assigned insectary in Bancoumana or Doneguebougou, mosquitoes are secured within the transporting containment. The insectary is adequately equipped with rooms with humidifiers which are regularly monitored according to standard insectary procedures, and access to the insectary is limited to study personnel only. After feeds, mosquitoes, still in net-sealed cups, are transported back to the insectary in Bamako. All subsequent handling of mosquitoes will take place in Bamako.

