15.4.5 Direct Skin Feeds

Risks associated with mosquito bites include mild to moderate swelling and itching at the site. Participants will be offered symptomatic treatment (i.e., local application of antipruritic agent) if these occur. While malaria and filarial parasites are transmitted through *Anopheles* mosquito bites as part of the parasite life cycle, mosquitoes raised in an insectary that are used for DSFs have never been exposed to human blood (breeding stocks are maintained on human blood as noted in **Section 9.5.2**) and since these parasites are not transovarially (vertically) transmitted in mosquitoes, there is no risk of transmission to participants. O'nyong'nyong virus is transmitted to humans by anopheles mosquitoes, but is not vertically transmitted so does not pose a risk of infection to subjects or the mosquito colony. Anopheles mosquitoes can rarely transmit rift valley fever (RVF) virus, and RVF has been reported to transovarially infect anopheles⁴⁴. RVF is primarily transmitted to humans by direct contact with infected animals, although transmission by mosquitoes can occur, with *Aedes* mosquitoes being the primary vector. The incubation period is 2-6 days.⁴⁵ No outbreaks of RVF have been reported in Mali, and transovarial infection is rare and extremely unlikely to persist for generations (for example, in a lab colony maintained at MRTC or elsewhere). To document the lack of viral contamination, the lab strain and field caught mosquitoes were tested for RVFV using molecular methods. Testing conducted over the last 2 years in Mali on LMIV/MRTC clinical trials have all been negative for RVFV. Because routine tests for this virus are not feasible, we installed a procedure to ensure that blood meals used to rear the mosquitoes are free of the virus (see **Section 9.5.2**).

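### The shortest permitted hold on donor blood for the mosquito colony (5 days) is one day less than the longest Rift Valley fever incubation the protocol states (6 days)

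*Combined protocol and SAP*

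**What the plan says.** Section 9.5.2 (Mosquito Rearing at the Insectary) explains that the colony used for direct skin feeds is maintained on blood from local healthy donors. Its waiting rule reads: "To ensure that the donor is free of potentially transovarial arbovirus in incubation, the donated blood is only used 5-7 days after the collection". A second condition for release is that the "donor is confirmed to remain healthy during this period". The section adds that arbovirus tests cannot feasibly be run routinely on donors, because access to positive controls is restricted. It also says that donor samples and colony mosquitoes are regularly tested for RVF in the US.

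Section 15.4.5 (Direct Skin Feeds, under Risks) says that "RVF has been reported to transovarially infect anopheles" and that "The incubation period is 2-6 days". Having noted that testing for it cannot be done as a routine, the section states: "we installed a procedure to ensure that blood meals used to rear the mosquitoes are free of the virus". It refers the reader back to Section 9.5.2 for that procedure. The same section reports no RVF outbreak in Mali, describes transovarial infection as rare and extremely unlikely to persist for generations, and states that testing over the last two years was all negative.

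**The concern.** A hold of this kind works by waiting until a donor who was infected at donation would have become ill. For that logic to hold throughout, the shortest permitted wait must be at least as long as the longest incubation. Section 9.5.2 lets blood be used from day 5, while Section 15.4.5 puts the longest RVF incubation at day 6. A donor with a long incubation can therefore still look healthy when the blood is released.

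RVF is the one virus for which Section 15.4.5 reports transovarial infection of Anopheles, and the hold is the procedure that section cites for keeping it out of the blood meals. What is at stake is whether a participant-safety measure for subjects undergoing direct skin feeds does what the protocol says it does. No endpoint, sample size or analysis depends on it.

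**Working it through.** The check is a comparison of two durations. The protocol gives no figure for how well the hold performs, so there is none to reproduce.

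**Inputs**
- Hold H: 5 to 7 days after collection (Section 9.5.2).
- Incubation L: 2 to 6 days (Section 15.4.5).
- Release condition: donor still healthy during the hold (Section 9.5.2).

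**Step 1. Shortest hold against longest incubation**
- H = 5: 5 − 6 = −1 day (short by one day).
- H = 6: 6 − 6 = 0 days (no margin).
- H = 7: 7 − 6 = +1 day.

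**Step 2. Who can pass**

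A donor infected u days before collection falls ill L − u days after collection. That donor passes a health check ending on day H if L − u > H. With H = 5 this requires L > 5 and u < L − 5, which is at most 1 day. For L of 2, 3, 4 or 5 days no donor passes. For L = 6 the window is one day. The blood must also be used between day 5 and day 6, because by day 6 the window has closed.

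**Step 3. Size, under an assumption**

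The documents give only the range of L. Take L as uniform on 2-6 days, with blood used on day 5.
- Donor infected at the moment of donation (u = 0): share with L > 5 is (6 − 5)/(6 − 2) = 25%.
- Donor at a random point of incubation at donation: share = mean of max(0, L − 5) divided by mean of L. The numerator is (1/4) × (1/2) = 0.125 days. The denominator is (2 + 6)/2 = 4 days. The result is 0.125/4 = 3.1%.
- With H = 6 or H = 7 both shares are 0%.

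**Step 4. Range over the assumption**

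If no incubation exceeded 5 days, the share of incubating donors who pass would be 0%. If every incubation lasted the full 6 days, it would be (6 − 5)/6 = 16.7%. The 3.1% lies between these extremes and depends on the assumed shape.

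All these shares are conditional on a donor who is already infected and incubating. They are not risks per blood unit or per participant.

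**The case against.** The strongest reply is that this is a one-day mismatch with almost no practical consequence. Section 15.4.5 reports no RVF outbreak in Mali, rare transovarial infection and negative testing, and names *Aedes* as the primary vector. That stands, and it is why the absolute risk is very small. It does not make the hold meet its stated aim, because neither section makes a test result a condition for releasing a blood unit.

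A second reply is that the health check may in practice run to day 7. Section 9.5.3 leaves further rearing details to study SOPs, so actual practice is unknown. The protocol text does not secure that reading, since it permits use from day 5.

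Several stronger readings are tempting but not supported:
- A reader might infer that the two sections contradict each other on testing. They do not: both say routine tests are not feasible and both describe some RVF testing outside routine donor screening.
- A reader might take 25% as the share of incubating donors missed. It applies only to infection at the moment of donation, and it assumes that blood drawn then already carries the virus, which no document says.
- A reader might gauge the risk by multiplying feeds by mosquitoes per feed. That product says nothing about the probability that a donor is infected, that the colony becomes infected, or that virus passes to offspring.
- A reader might infer that participants are told something untrue. The consent pages are not among the documents reviewed, so this cannot be checked.

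**Conclusion.** The inconsistency is real and narrow: at the 5-day end of its range, the hold is one day shorter than the longest incubation the protocol gives for the virus it is meant to exclude. From 6 days on the gap closes, with no margin at exactly 6. The estimate of about 3% of incubating donors rests on uniform incubation and uniform time since infection, neither of which is in the documents. The 0% at 6 days or more assumes that an infected donor becomes recognisably ill within the stated incubation, which the documents do not say either. The point is worth correcting because the protocol presents the procedure as assurance of virus-free blood meals. It is not evidence of material danger to participants.

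**What to change.** Reconcile Section 9.5.2 with Section 15.4.5 so that the shortest permitted hold, and the donor health check that ends it, is not shorter than the longest incubation the protocol states. The existing health check needs no new procedure; its end point only needs to be tied explicitly to that duration. Part of the current 5-7 day range already satisfies the condition. If this is not operationally possible, soften *ensure* in both sections so that the hold is described as reducing the chance of an incubating donor rather than excluding it.

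The cost is about one sentence in each section and a matching change to the insectary SOP. The downside is colony blood meals up to a day or two older, still within the range already allowed.
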